9.3.1. Study visits

- Selection/Randomization.
- Day 4-6 (any day between 4 and 6).
- Day 12-16 (any day between the 12th and the 16th).
- Day 28 (window allowed: day 24 to day 30).
- 3 months (window allowed: ± 2 weeks). This visit can be made in person or by telephone at medical discretion, depending on the patient's condition and the usual practice of the center.
- Visit to discharge or premature withdrawal. This visit can be done in person or by telephone.

9.3.2. Study Procedures

- **Chronopathology of COVID-19 infection.** During the screening visit, the date of onset of symptoms and the date of the first confirmatory diagnostic test

will be collected. In addition, if the diagnostic RT-PCR was not performed in the last 10 days, it will be necessary to repeat it and confirm the positivity.

- **Medical history comorbidities** (including hypertension, diabetes mellitus, dyslipidemia, heart failure, ischemic heart disease, stroke, chronic obstructive pulmonary disease, bronchial asthma, hypopnea sleep apnea syndrome, hypoventilation, chronic kidney disease, chronic liver disease, neoplasia, transplant, human immunodeficiency virus infection, autoimmune disease, dementia, smoker)
- **Clinical evaluation of COVID**, assessment of own symptoms, date of onset of symptoms and evolution of them.
- **WHO scale** of 10 categories (Annex 1).
- **Physical examination** (includes general assessment of the patient, degree of hydration, nutrition, vital signs and respiratory situation, cardiopulmonary auscultation, abdominal examination and a neurological assessment of alertness).
- **Concomitant medication** registration (start and end date, active substance and dose).
- **Biochemistry and blood count** (determination of blood count, coagulation with D-dimer, biochemistry including creatinine, ions, AST, ALT, BT, BD, LDH, PCR, ferritin, blood gases and IL-6).
- **Adverse events**, medication-related or non-medication-related.
- **Chest X-ray (X-ray) or Computed Tomography (CT)** (Brixia scale – Annex 1).
- **Electrocardiogram (ECG), according to** the usual practice of the center.
- Both the 3-month follow-up visit and the premature withdrawal visit can be done in person or by telephone. If the visit is carried out in person, in addition to the assessment of the COVID clinic, the registration of concomitant medication and the registry of adverse events, the following procedures would be carried out:
 - WHO scale of 10 categories (Annex 1).
 - Physical examination.
 - Biochemistry and blood count.

- Chest X-ray (X-ray) or Computed Tomography (CT) (Brixia¹² scale – Annex 1).

10. Study variables and parameters

10.1. Variable Principal:

- Death after 28 days

10.2. Secondary Variables

- Admission to the Intensive Care Unit at 28 days
- Need for noninvasive mechanical ventilation or high-flow oxygen at 28 days.
- Need for mechanical ventilation and intubation at 28 days.
- Use of other immunosuppressive drugs.
- Time to discharge (days of hospitalization from start of treatment)
- Baseline at 3 months of treatment according to the WHO 10-category scale .

11.2. Data Management

11.2.1. Electronic Data Collection Notebook (CRDe)

The data collected will be recorded in an electronic Data Collection Notebook (CRDe), whose veracity will be validated by the designated monitors. In the CRD, each patient will be identified by an alphanumeric code that identifies the patient. At all times, the data protection provisions of Organic Law 3/2018 on the Protection of Personal Data and guarantee of digital rights will be respected.

11.2.2. Identification

Each patient receives an identification number when randomized. Only the pharmacy and principal investigator at each facility know the correspondence between the study identification number and the patient's medical record number (NHC).

It corresponds to the principal investigator of each center, who will be responsible for maintaining the list with the allocation of patients and their medical history number.

11.2.3. Record in medical records

Participation in the study will be included in the evolution of the clinical history of each center. All study data shall be recorded in the study so that all data collected in the CRDe can be verified. The data will be obtained from the personal interview with the patient and access to their complete medical history.

In the event that the patient does not attend any of the planned visits, the researcher will contact him by telephone to confirm that this absence is not due to a conscious abandonment of the follow-up. If you do not contact him, you will access the local or regional digital medical record to know if there have been events related to the study that have been evaluated in another health center.

11.3. Statistical analysis

The categorical variables will be presented as frequency and percentage and the continuous variables as mean and standard deviation.

Death after 28 days, intubation or admission to the ICU will be presented as proportions. The difference in proportions will be estimated with a 95% confidence interval.

An analysis per protocol will be performed, considering those patients who have received at least 2 doses of the assigned drug. In addition, an intention-to-treat analysis will be carried out.

In the event that there is a depletion of stock and any of the guidelines are replaced by one of the alternatives proposed in point 8.2, no adjustment would be made in the analysis since the equivalence of dose and dosage between the original dose and the substitution is established.

For the analysis of the main outcome, death at 28 days, survival analysis will be performed and the Hazard ratio of the Cox regression, with the log-rank statistic, will be used to estimate the mortality relationship.

An alpha error of 5% is set.

In case there was a lack of balance in the age of the patients between the groups, age-adjusted analyses would be performed, establishing 2 groups: < 70 years and \geq 70 years.

Two interim efficacy and safety analyses are established with 100 and 200 patients

2 analyses of the results are established according to:

- a) Time of evolution (<7 days from the onset of symptoms, \geq 7 days from the onset of symptoms).
- b) Presence of a state of high inflammation. The patient is considered to have a high degree of inflammation when he meets any of the following laboratory criteria:
 - Ferritin greater than or equal to 1000 mg/dl
 - IL-6 greater than or equal to 20 pg/ml
 - PCR mayor o igual a 150 mg/l
 - D-dimer greater than or equal to 1000 mg/dl

Finally, since no age criterion is established to exclude older patients, a sensitivity analysis will be performed, leaving out those patients who had orders of no intubation or non-invasive mechanical ventilation prior to being included in the study.

For statistical analysis, the IBM SPSS statistics, version 21 program will be used.

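### The secondary escalation outcomes (ICU admission, NIV or high-flow oxygen, intubation) ignore death as a competing event, so their between-arm differences can be diluted or, under some assumptions, reversed

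*Combined protocol and SAP*

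**What the plan says.** Section 10.1 makes 28-day death the primary variable. Section 10.2 then lists the escalation outcomes one by one, including "Admission to the Intensive Care Unit at 28 days" and "Need for mechanical ventilation and intubation at 28 days", with NIV or high-flow oxygen as a further item. None of them includes death.

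Section 11.3 gives the analysis: "Death after 28 days, intubation or admission to the ICU will be presented as proportions", followed by "The difference in proportions will be estimated with a 95% confidence interval". Time-to-event methods are specified for death alone: "For the analysis of the main outcome, death at 28 days, survival analysis will be performed". The document contains no combined escalation-or-death outcome and no competing-event method. It gives no denominator, and no rule for a patient who dies without reaching ICU or being intubated.

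Two provisions come close to the point:

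- Section 11.3, noting that older patients are not excluded, plans a sensitivity analysis "leaving out those patients who had orders of no intubation or non-invasive mechanical ventilation prior to being included in the study".
- The WHO scale in Annex 1 scores death as 10 and is recorded at several visits (section 9.2), but section 10.2 makes it an outcome only at 3 months.

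**The concern.** The hypothesis in section 5.1 covers fewer deaths and also less need for intubation or ICU, and section 5.3 makes respiratory support a secondary objective. The escalation outcomes will therefore be read as evidence of efficacy.

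Death without escalation prevents the escalation event from ever being observed. In a plain proportion over all patients, such a death adds to the denominator and not to the numerator. If the treatment works as hoped, the control arm has more of these deaths, and its ICU and ventilation rates look lower than its patients' true course. The treatment difference on those outcomes shrinks. It can change sign if patients spared a ward death go on to need ICU. A reader could then conclude that the bolus regimen has little effect on escalation, or increases it, when patients on it are faring better.

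**Working it through.** **Inputs from the plan (section 11.1).** Expected 28-day mortality is 23% (RECOVERY) and 10% (BOLUS), with alpha 5%, power 80% and 145 per arm. I assume a two-sided test, since sidedness is not stated.

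**The plan's own figure.** A two-sided comparison of 23% with 10% at 80% power needs 142 per arm with continuity correction and 127 without. The stated 145 is close to the corrected figure. Uncorrected power at 145 per arm is 85%. The mortality sample size is not in question here.

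**Expected deaths.** 145 × 0.23 = 33.4 and 145 × 0.10 = 14.5. The competing event is more than twice as frequent in the control arm under the plan's own assumption.

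**Assumptions not in the documents.** Let f be the share of deaths that occur without ICU admission, and let 10% of survivors reach ICU in both arms. With p for mortality:

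- ICU admission = p(1 − f) + (1 − p) × 0.10
- ICU admission or death = p + (1 − p) × 0.10

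| f | ICU, RECOVERY | ICU, BOLUS | Difference, points (95% CI at 145 per arm) |
|---|---|---|---|
| 20% | 0.184 + 0.077 = 26.1% | 0.080 + 0.090 = 17.0% | 9.1 (−0.3 to 18.5) |
| 50% | 0.115 + 0.077 = 19.2% | 0.050 + 0.090 = 14.0% | 5.2 (−3.3 to 13.7) |
| 70% | 0.069 + 0.077 = 14.6% | 0.030 + 0.090 = 12.0% | 2.6 (−5.2 to 10.4) |

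ICU admission or death is 0.230 + 0.077 = 30.7% versus 0.100 + 0.090 = 19.0%, a difference of 11.7 points (1.8 to 21.6) whatever f is. The gap between the two measures is f × (23 − 10) points: 2.6, 6.5 and 9.1 in the three rows.

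**Other survivor ICU rates.** For f from 30% to 70% and survivor ICU rates from 5% to 20%, the ICU-only difference runs from 1.3 to 8.5 points and the combined difference from 10.4 to 12.3. The combined difference is the larger throughout.

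**Can the sign change?** Two constructed cases show that it can.

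1. Take f = 70%, and suppose half of the patients whose deaths are averted (13% of the arm) need ICU, while the other 77% keep the 10% rate. BOLUS ICU admission is 0.10 × 0.30 + 0.77 × 0.10 + 0.13 × 0.50 = 0.030 + 0.077 + 0.065 = 17.2%, against 14.6% on RECOVERY. ICU admission or death is 0.100 + 0.077 + 0.065 = 24.2% against 30.7%. The extra 0.065 term raises the BOLUS survivor ICU rate to 0.142 / 0.90 = 15.8%, so this case departs from the equal-rate assumption above. The 2.6-point reversal would be detected with only about 9% power.
2. Hold ICU admission or death equal at 30% in both arms, with f = 75%. ICU admission alone is 0.30 − 0.75 × 0.23 = 12.8% versus 0.30 − 0.75 × 0.10 = 22.5%. BOLUS looks worse by 9.8 points (95% CI 1.1 to 18.4) although the combined outcome is identical.

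**The case against.** The strongest reply is that nothing is hidden. Death is the primary outcome, has its own Cox and log-rank analysis, and is reported beside intubation and ICU admission. A patient who dies on the ward is a failure on the outcome that decides the trial. This stands, and it confines the point to the secondary outcomes. A reader might infer that the plan counts a ward death as a good result. It does not say so: the non-event status is the default of a plain proportion, and the plan states no coding rule or denominator. Separate marginal proportions still do not show how many deaths occurred without escalation, so the reader cannot correct for them.

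A second reply is that the plan foresaw the issue. The sensitivity analysis removes patients with earlier orders against intubation or NIV, and the exclusion criteria remove those thought likely to die within 24 hours and those with moderate to severe dementia. This narrows the problem. It does not cover limits set after inclusion or unexpected ward deaths, and the main analysis is unchanged. The documents give no frequency for either.

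A third reply is that the size rests on assumed inputs. That is correct. At a 20% share of deaths without ICU the loss is modest (9.1 against 11.7 points); it becomes large only at higher shares.

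Finally, a reader might infer that the combined outcomes are better efficacy measures because they have more power: 64% against 22% for ICU alone at f = 50%. In this model the treatment does not change ICU use among survivors, so the gain is imported mortality, and mortality alone has 85% power. The figures do not support letting the combined outcomes carry efficacy claims.

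**Conclusion.** The concern holds for the three secondary escalation outcomes. As planned, they do not account for death without escalation, and the expected mortality of 23% versus 10% makes that event unbalanced between arms. With 10% ICU admission among survivors in both arms, the ICU difference falls to 9.1, 5.2 or 2.6 points at 20%, 50% or 70% of deaths without ICU, against 11.7 points for ICU admission or death. Both the 10% and the shares are assumptions. The same mechanism applies to intubation and to NIV or high-flow oxygen, for which I give no separate figures.

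Reversal is possible only under further assumptions, such as many averted deaths needing ICU or a high share of deaths outside ICU. The documents do not show that it is likely. Nor do they support reading the quoted sentence in section 11.3 as a composite, because section 10 lists the variables separately. The primary analysis and the sample size are unaffected.

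**What to change.** In section 11.3, for each escalation outcome in section 10.2, add a supplementary comparison of event or death by day 28: ICU admission or death, NIV or high-flow oxygen or death, and intubation or death. Use the difference in proportions with a 95% confidence interval already planned, and state the denominator. Beside each, show the component proportions and the number of deaths without that escalation by arm. State that the escalation proportions will not be interpreted without these figures.

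The cost is wording and table layout: death and each escalation event by day 28 are already study variables, and the sample size does not change. The downside is that mortality partly drives the combined outcomes. The components must stay visible, and the three added comparisons should be labelled supportive, not a new basis for efficacy claims. Cumulative incidence of escalation with death as a competing event would be a reasonable additional display, provided the deaths without escalation are still reported by arm.

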7.3. Criteria for withdrawal of subjects.

- Voluntary patient abandonment: patients have the right to withdraw from the study at any time and for any reason, being able to express it personally or through their representative.
- By medical criteria (safety and efficacy):
 - that it is necessary to adopt new treatments due to the presence of serious adverse events that may be related to the use of corticosteroids such as severe infection of bacterial origin, etc.

- the deterioration of this is severe and it is considered necessary to replace the administered corticosteroid or initiate additional immunosuppressants or immunomodulators.
- That there is scientific evidence that supports the administration of new treatments that change the prognosis of patients and force them to modify the standard treatment of these.
- For non-compliance or violation of the rules contained in the protocol: when the patient no longer complies with the rules or procedures established in this protocol or there is loss of follow-up.

All patients who, regardless of the cause and stage of the study in which they are, prematurely and permanently discontinue treatment or follow-up, should complete the premature withdrawal visit, which will take place within 24-48 hours of becoming aware of withdrawal.

7.4. Premature discontinuation of the Study.

This study may be temporarily interrupted or terminated prematurely if in the opinion of the sponsor there is sufficient reasonable cause. The investigator will receive written notice that the terminating party documents the reason for the suspension of the study.

The circumstances justifying the suspension of the present study include, but are not limited to:

- (a) Identification of unforeseen, substantial or unacceptable risks to patients.
- (b) Inability to enroll an acceptable number of patients.
- (c) Insufficient compliance with the requirements of the protocol.
- d) Plans for modification, suspension or discontinuity of the development of the study drug.
- e) Administrative reasons that the promoter could not solve with the health authorities.
- f) The study is interrupted if scientific evidence appears to support the administration of new treatments that change the prognosis of patients and force them to modify the standard treatment of these.

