8.4. Concomitant treatments

8.3.1. Concomitant treatment allowed (Standard Treatment)

Although this is a pragmatic study in real practice and some degree of heterogeneity is accepted in standard treatment, minimum requirements are considered to be able to include patients in the study. Thus, as standard treatment is accepted:

- a) Supplemental oxygen. For use in patients with hypoxemia. The target for oxygen therapy should not exceed 92% in patients at risk of respiratory failure with hypercapnia and 96% in all other patients.
- b) Antibiotic treatment. Standard treatment protocols should not recommend the administration of empirical antibiotic treatment on a routine basis. Its administration should only be recommended when risk of bacterial pneumonia is considered as co-infection. The antibiotic regimen will correspond to the usual treatment guide of the center.
- c) Prophylaxis or thromboembolism treatment with low molecular weight heparins. Thrombotic prophylaxis is recommended in all admitted patients and the use of therapeutic doses in patients with confirmed thromboembolic disease. The use of extended prophylaxis guidelines could be assessed according to the recommendations of the Spanish society of thrombosis and hemostasis.

- d) Remdesivir. The use of remdesivir is accepted if it is done according to the recommendations of the Ministry of Health.
- e) Other antiviral drugs or drugs that block viral activity. The protocols should not incorporate the following drugs: Hydroxychloroquine or chloroquine, lopinavir-ritonavir.
- f) Serum therapy. The use of serum therapy is allowed in those indications defined in the protocols.
- g) Other concomitant medications without antiviral or immunosuppressive effect (eg: antihypertensives, analgesics, lipid-lowering agents, antiplatelet agents,...). There is no limitation to the use of these drugs.

8.3.2. Concomitant treatments prohibited.

Other immunosuppressants. The concomitant use of other immunosuppressants is NOT allowed in the first 48 hours of evolution. If immunosuppressants are prescribed during the study, patients in whom they are initiated with the third or subsequent dose of CG should be maintained. The use of these drugs in these patients will be considered as an event.

9. Development of the study.

9.1. Study schedule.

Recruitment is planned to begin in December 2020.

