12.10. Reporting of Serious Adverse Events

The principal investigator or collaborator shall report to the Pharmacovigilance Department FV-UICEC-HUC, all serious adverse events (as defined below), whether or not considered treatment-related or expected, within **24 hours** (one working day), of their knowledge and through the corresponding notification form. Serious adverse events occurring should be reported at any time after the patient is included in the study (defined as the time the subject signs informed consent) and up to 30 days after the subject concludes or leaves the study. A subject is considered complete: after the conclusion of the last visit or contact (e.g., telephone contact with the investigator or a collaborator),

as indicated in the protocol assessment schedule, or after the last dose of study medication, whichever is later. Withdrawal is defined as the date on which a subject and/or investigator determines that the subject can no longer meet the study requirements at any subsequent visits and assessments.

The reporting investigator will complete and sign the AAG notification form for the study that will be faxed or emailed to:

PhD [name]

Head of Pharmacovigilance UICEC of the University Hospital of the Canary Islands (HUC)

[contact] [contact]

Email: [contact]

PV staff will review the form received and, if appropriate, request additional information from the investigator. The investigator will provide information to the sponsor or to whoever assumes the tasks delegated by the sponsor (FV-UICEC-HUC Unit) whenever requested and, in any case, when his initial assessment changes in terms of severity or causality. The reporting of follow-up information shall follow the notification procedure described above.

The staff of FV-UICEC-HUC shall keep a detailed record of all AAGs or of special interest communicated to them by investigators.

In the event of a medication error or the investigational medicinal product is used outside the provisions of the protocol during the development of the study, the investigator will notify the FV-UICEC-HUC within 24 hours of becoming aware of it. The circuit for notification and form will be the same as for AAGs.

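### Section 11.3 does not say whether ITT or per-protocol is the primary analysis of 28-day death, and section 7.3 leaves unclear whether patients withdrawn for deterioration are followed to that endpoint

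*Combined protocol and SAP*

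**What the plan says.** **Analysis sets (11.3).** The per-protocol analysis comes first: "An analysis per protocol will be performed, considering those patients who have received at least 2 doses of the assigned drug". The next sentence reads "In addition, an intention-to-treat analysis will be carried out". For the main outcome, the "Hazard ratio of the Cox regression, with the log-rank statistic, will be used to estimate the mortality relationship". That paragraph names no analysis set and no censoring rule, and no other section ranks the two sets.

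**Withdrawal (7.3).** One of the medical criteria for withdrawing a subject is that "the deterioration of this is severe and it is considered necessary to replace the administered corticosteroid or initiate additional immunosuppressants or immunomodulators". Patients who permanently "discontinue treatment or follow-up, should complete the premature withdrawal visit, which will take place within 24-48 hours" of the withdrawal becoming known. Nothing is said about vital status after that visit.

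**Other sections on the same patients.**
- 8.3.2, on added immunosuppressants: "patients in whom they are initiated with the third or subsequent dose of CG should be maintained". Their use is counted as an event.
- 10.2 lists use of other immunosuppressive drugs as a secondary variable.
- 12.13 keeps patients who stop study drug in the trial and follows them to its end.
- 12.10: "Withdrawal is defined as the date on which a subject and/or investigator determines that the subject can no longer meet the study requirements" at later visits. It also requires serious events to be reported "up to 30 days after the subject concludes or leaves the study".
- 11.2.3 gives access to the full medical history, and to local or regional records when a patient misses a visit and cannot be contacted.

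**The concern.** The per-protocol set is formed after randomisation. Anyone who dies or stops before the second dose leaves it. Two doses are 2 of 3 in the bolus arm and 2 of 10 in the dexamethasone arm, so the set does not mean the same thing in both. With neither set named as primary, the headline result can be chosen once the data are known.

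The second issue concerns the patients most likely to die. If a site takes 7.3 to end follow-up, a deteriorating patient is censored shortly before the endpoint, or left out. The Cox and log-rank methods assume that censoring is unrelated to prognosis, and here it would be closely related. The trial is open-label, so physicians who know the arm decide when to change treatment, and losses could differ by arm. The direction of any bias cannot be known in advance.

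**Working it through.** **1. The plan's own figure.** Inputs from 11.1: mortality 23% v 10%, alpha 5% (two-sided assumed), power 80%. With mean proportion 0.165, the pooled two-proportion formula gives

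n = [1.960·√(2·0.165·0.835) + 0.842·√(0.23·0.77 + 0.10·0.90)]² / 0.13² = 126.8, so 127 per arm.

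With continuity correction, n' = (n/4)·[1 + √(1 + 4/(0.13n))]² = 141.8, so 142 per arm, within 3% of the stated 145. Sample size is not at issue.

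**2. Passages on a patient who deteriorates and starts an immunosuppressant.**

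| Section | Bearing on follow-up |
|---|---|
| 7.3 | Subject-withdrawal criterion; one visit at 24-48 h; stopping treatment and stopping follow-up named as alternatives |
| 8.3.2 | From the third dose, patient maintained (the translation does not say in what); use is an event |
| 10.2 | Use is an outcome |
| 12.13 | Followed to the end after stopping drug; headed as discontinuation for adverse events, but the permanent-stop criteria include investigator opinion |
| 12.10 | Serious events reported for 30 days after leaving |

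The last four fit continued observation. Section 7.3 can be read either way.

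**3. Lost deaths with no true effect.** Take 23% mortality in both arms and 145 per arm, so 0.23·145 = 33.35 expected deaths each. Assume a share f of one arm's deaths is lost through withdrawal and that withdrawn patients have mortality m. Then f·33.35 deaths leave the numerator and f·33.35/m patients leave the denominator.

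Example, 0% v 20% lost, m = 100%: arm 1 has 33.35/145 = 0.230; arm 2 has 26.68/138.33 = 0.1929. The difference is 0.0371, the pooled SE 0.0486 and the unpooled SE 0.0484. Rejection = 1 − Φ[(1.960·0.0486 − 0.0371)/0.0484] + Φ[(−1.960·0.0486 − 0.0371)/0.0484] = 11.5% + 0.3%, or 11.85% before rounding.

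The log-rank figures come from 10,000 simulated trials per case. Death times are exponential, lost deaths are censored 1-7 days before death, and withdrawn survivors are censored uniformly over days 0.5-24. With no loss the simulation rejects 4.9%.

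| Deaths lost (arm v arm) | z-test, m = 100% | z-test, m = 50% | z-test, m = 23% | log-rank, m = 100% | log-rank, m = 50% |
|---|---|---|---|---|---|
| 0% v 5% | 5.4% | 5.2% | 5.0% | 5.4% | 5.4% |
| 0% v 10% | 6.6% | 5.8% | 5.0% | 7.1% | 6.1% |
| 0% v 20% | 11.9% | 8.5% | 5.0% | 12.1% | 10.8% |
| 10% v 20% | 6.8% | 5.9% | 5.0% | 7.0% | 6.5% |
| 20% v 50% | 28.3% | 18.8% | 5.0% | 31.0% | 26.2% |

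At m = 100%, a true hazard ratio of 1 reads as 0.95, 0.90, 0.81, 0.89 and 0.63 down the rows.

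The handling convention also matters. Keeping withdrawn patients in the denominator as survivors turns the 6.8% for 10% v 20% into 7.8%.

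**4. Power at the planned effect (23% v 10%, log-rank, m = 100%).** Equal losses of 10% or 25% of deaths lower power from 86% to 83% or 75%, with the hazard ratio staying near 0.40. Losing 5%, 10% or 20% of control deaths only gives 81%, 75% or 58%.

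**5. Choosing between the two sets.** Simulation of 400,000 trials with no true effect (23%); a share of each arm falls outside the per-protocol set, and a positive result is claimed if either z-test is significant. At 2%, 5% and 10% excluded per arm, the false-positive rate is about 6%, 6-6.5% and 6.6-7.1% (mortality among the excluded 23% to 50%). Excluding 10% in one arm only, with 50% mortality, gives 11%. Per-protocol alone then already rejects 9.2%, so most of that excess is bias in the set and not freedom to choose.

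**The case against.** The strongest reply concerns follow-up. Section 7.3 nowhere says that follow-up stops, and it treats stopping treatment and stopping follow-up as different things. Read with 12.13, it keeps these patients under observation. The withdrawal definition in 12.10 serves to fix the serious-event window and does not govern endpoint follow-up. That window, 30 days after leaving, runs past day 28 for every randomised patient. Many deteriorating patients are likely still to be inpatients whose records the site holds. Losing a large share of deaths would therefore need widespread failure to report.

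Much of this stands. A reader might infer that 7.3 removes deteriorating patients from the endpoint; the text does not support that. Nor does placing per-protocol first make it the primary analysis, since the plan does not say so. What remains is that serious-event reports go to pharmacovigilance and are not linked to the endpoint. The adverse-event definition in 12.1, which sets apart worsening of the disease under study, could be read to leave out COVID progression. The record search in 11.2.3 is triggered by a missed visit, not by a 7.3 withdrawal. Even when the death is known, no rule says whether a death after withdrawal counts.

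On the analysis set, exclusion 1 (expected death within 24 hours) should limit how many patients miss the second dose, so the effect of choosing between sets is probably small. That limits the size of the problem; it does not supply the missing choice.

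**Conclusion.** The concern holds in this form: no primary analysis set or censoring rule is named for a mortality endpoint, and 7.3 is ambiguous about follow-up of patients at high risk of death. Confidence is high on the first and moderate on the second.

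Every loss share is an assumption. Small losses do little harm: 5-10% of deaths lost in one arm gives about 5-7% false positives. A 20% loss in one arm gives about 8-12%. On the z-test there is no inflation if withdrawn patients have average mortality. The 20% v 50% case (19-31%) is an extreme illustration that nothing in the documents supports, and it should not be read as an expected error rate. Choice between the two sets adds one to two percentage points with equal exclusion.

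The need to correct does not rest on a large expected bias. It rests on the primary mortality analysis being open to choice after the data are seen, and on a follow-up rule that sites can apply differently in an open-label trial.

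**What to change.** **In 11.3:**
- Make ITT the primary analysis: all randomised patients, as assigned, deaths to day 28 whatever treatment followed.
- Make the Cox/log-rank test in that set the single primary test. Report the difference in proportions in the same set as a supporting estimate, and per-protocol as supportive. This leaves one headline result.
- Censor at day 28, or at last known alive only if consent to follow-up is withdrawn or vital status cannot be found.

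**In 7.3:** state that the medical withdrawal criteria do not end follow-up, and that day-28 vital status is obtained for every randomised patient from the records already used under 11.2.3, unless consent to follow-up is withdrawn.

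**Across sections:** reconcile 7.3 with 8.3.2 and 12.13 without changing any treatment rule.

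**Cost:** a few sentences, and a short day-28 record check for each withdrawn patient. The sample size stays at 290, with no added visits or procedures.
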